7.4.2. Secondary Efficacy Analysis

The following variables will be analyzed to determine whether they follow a normal distribution: number of exacerbations, duration of the episodes, need for antibiotic therapy, number of hospital admissions, duration of the hospital admissions, immunological outcomes described in the trial design, quality of life, and direct costs.

These variables will be described together with their mean and standard deviation, or, in case of asymmetry, with their median and interquartile range. Differences between the means will be analyzed using Student's T test in the case of variables with a normal distribution and Mood's median test in the case of variables without a normal distribution. The absolute effect (difference in estimators) and its precision will be estimated with a 95% confidence interval (CI) in all cases.

The appearance of the first exacerbation will be studied at 3, 6, 12 months and whole study in the intention to treat (ITT) and per protocol (PP) sets and these same limits will be studied in the moderate and severe COPD populations. The appearance of any exacerbation at 3, 6, 12 months and whole study will be studied in the ITT and PP sets.

Number of exacerbations will be studied in the mild, moderate and severe COPD populations at 3, 6, 12 months and whole study. Number of exacerbations in the ITT and PP sets will be studied at 3, 6, and 12 months.

To compare the change in the immunological variables described in the trial design at 0, 3, 6, 12, and 18 months, an analysis of covariance will be performed, estimating the mean difference over time in both study groups.

The cost-benefit ratios in the study groups will be estimated together with their 95% CI, and compared using non-parametric tests.

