### **10. STATISTICS**

#### **10.1. Description of the Statistical Methods to be Used, Including the Schedule of any Planned Interim Analysis**

The study analysis will be performed after the database lock. The intention-to-treat (ITT) population will be composed of subjects who took at least one dose of the trial medication. The analysis will be performed on both the ITT and per-protocol populations.

The randomization will be evaluated by comparing the baseline variables (month 0) in both study groups according to the Consolidated Standards of Reporting Trials (CONSORT) due to their clinical relevance. Qualitative variables will be reported together with their frequency distribution, and quantitative variables will be reported together with their mean and standard deviation, or, in case of asymmetry, with their median and interquartile range. If confounding is detected, the effects will be adjusted with the potentially confounding variables using the appropriate model adjustments.

The following variables will be analyzed to determine whether they follow a normal distribution: number of exacerbations, duration of the episodes, need for antibiotic therapy, number of hospital admissions, duration of the hospital admissions, immunological outcomes described in the trial design (page 67), quality of life, and direct costs.

These variables will be described together with their mean and standard deviation, or, in case of asymmetry, with their median and interquartile range. Differences between the means will be analyzed using Student's T test in the case of variables with a normal distribution and Mood's median test in the case of variables without a normal distribution. The absolute effect (difference in estimators) and its precision will be estimated with a 95% confidence interval (CI) in all cases.

The rate of exacerbations per patient and the severity of these exacerbations will be compared using the chi-square test or Fisher's exact test. The relative risks will be estimated together with their 95% CI. The number needed to treat (NNT) or number of events prevented per treatment will be estimated.

The rate of episodes occurred over time will be calculated, and the hazards ratio (HR) will be estimated together with its 95% CI following a Cox proportional-hazards model. The NNT (number of patients that need to be treated to avoid an event) will also be estimated.

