5.1.2. Intention to Treat Set or Full Analysis Set (FAS)

All randomized subjects who have taken at least one dose. These subjects will be assigned to the corresponding treatment group.

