6.1.2. Secondary outcomes

- ★ Decrease in the rate of COPD exacerbations per study group at 12 months (end of the trial treatment) and 6 months after the trial's termination (follow-up).
- ★ Decrease in the severity of the COPD exacerbations. The severity of the exacerbations will be measured based on the consumption of healthcare resources (i.e., visits to the Emergency Department, hospitalizations, or consultations), as follows:
 - ICU hospitalization: 4 points.
 - Standard hospitalization: 3 points.
 - Emergency Department visit: 2 points
 - Consultation involving a change in the patient's usual treatment: 1 point.
- ★ Time elapsed between the start of the treatment and the first COPD exacerbation
- ★ Use of drugs (antibiotics, corticosteroids, etc). Drug consumption will be scored as follows:
 - Use of antibiotics: 1 point.
 - Use of inhaled corticosteroids: 2 points.
 - Use of systemic corticosteroids: 3 points.
 - Use of oxygen therapy: 4 points.
 - Use of mechanical ventilation: 5 points.
- ★ Number of hospitalizations due to COPD exacerbations.
- ★ Days of hospitalization due to COPD exacerbations.
- ★ Number of visits to the Emergency Room.
- ★ Number of unscheduled medical consultations due to COPD exacerbations.
- ★ Health-related quality of life, as determined by an adapted version of the specific CAT test.
- ★ Healthcare expenditure resulting from resource consumption during episodes of COPD exacerbations occurring during the trial period.
- ★ Variations (change between the baseline level and months 0, 3, 6, and 12, as well as in comparison with the placebo) in the following immunological parameters in the patients participating in the immunological substudy (N = 60) and/or those of the subgroup of the induced sputum study (N = 20) (between month 0 prior to the administration of the vaccine and month 12).

In the case of patients participating in the IMMUNOLOGICAL SUBSTUDY (n = 60), changes in the below parameters will also be assessed during the randomization visit (visit 1) and the visits corresponding to months 3, 6, and 12:

- The specific humoral response [REDACTED]
- The in vitro proliferative response of specific T cells [REDACTED]

In a subgroup of patients (n = 20) selected from the group of patients participating in the immunological substudy (n = 60), the following parameters will also be evaluated in samples of induced sputum at month 0 (visit 1) and month 12:

- ★ IgA response to Bactek antigens assessed using ELISA technique.

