7.1.2. Handling of Missing Data

No imputation of data will be carried out in case of missing data, but all available data will be used to its full extent.

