7.4. Efficacy Evaluation

The efficacy analyses will be conducted based on all the analysis sets.

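### Hospital days for COPD exacerbations are a listed outcome without a defined analysis; SAP 7.4.2 tests an unspecified duration of admissions that can hide or distort an effect on them

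*SAP*

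**What the plan says.** The outcome list in SAP 6.1.2 contains "Days of hospitalization due to COPD exacerbations". Protocol 5.1 and 8.1 use the same words.

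The analysis text does not use them. SAP 7.4.2 lists, among the variables to be checked for normality and then compared, "duration of the episodes, need for antibiotic therapy, number of hospital admissions, duration of the hospital admissions". The matching list in protocol 10.1 includes "need for antibiotic therapy, number of hospital admissions, duration of the hospital admissions". Both lists also contain a duration of episodes, which is not among the outcomes in protocol 5.1 or SAP 6.1.2.

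The comparison is by "Student's T test in the case of variables with a normal distribution and Mood's median test in the case of variables without a normal distribution".

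On who is analysed, SAP 7.4 says "The efficacy analyses will be conducted based on all the analysis sets", and SAP 5.1.2 defines the FAS as "All randomized subjects who have taken at least one dose". On gaps in the data, SAP 7.1.2 says "No imputation of data will be carried out in case of missing data".

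Neither document says whether the duration is per admission or a total per patient, what value a patient without an admission receives, or whether only admissions for COPD count.

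**The concern.** The listed outcome is a burden per patient: how many days each randomised patient spent in hospital because of exacerbations. The analysed variable is worded as a property of admissions. Because it stands next to a separate count of admissions, the pair reads most naturally as how many and how long, and a patient who was never admitted has no stay to measure.

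On that reading, the comparison is confined to a subgroup formed after randomisation by an event that the vaccine is meant to prevent. The two subgroups are no longer randomised groups. The variable can then show no difference, or longer stays on vaccine, in a trial where total hospital days fell.

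The other reading, total days with zeros, keeps the randomised groups but meets a different difficulty. Most values may be zero and follow-up will differ between patients, and the two planned tests suit neither feature.

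**Working it through.** **No plan figure to reproduce.** The documents give no admission rate, length of stay or expected effect on hospital days. The 90 per group in SAP 7.1.1 rests on exacerbations and does not bear on this point. Every admission figure below is an assumption, shown over a range.

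**Step 1. Three invented patients.** A has three 6-day stays, B one 10-day stay, C none.
- Total days per patient: 18, 10, 0.
- Mean length of stay: 6, 10, no value.

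The order of A and B reverses and C drops out. Averaging within a patient is itself one possible choice; the SAP names none.

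**Step 2. Length of stay against days per patient.** Let p be the share admitted and m the mean hospital days among those admitted. Days per randomised patient = p × m; the mean among the admitted = m. Assume that the vaccine halves p. For 30% v 15% and m = 8:
- days per patient 0.30 × 8 = 2.4 v 0.15 × 8 = 1.2;
- days among the admitted 8 v 8.

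If mainly shorter stays are prevented, so that m is 10 on vaccine:
- days per patient 2.4 v 0.15 × 10 = 1.5, a fall of 37.5%;
- days among the admitted 8 v 10.

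Rejection rates (%) at two-sided 0.05 come from 4,000 simulated trials per row, with 90 per arm, gamma-shaped stays and full follow-up:

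| Admitted, placebo v vaccine | Mean stay | Days per randomised patient | Admitted only: t / Mood | Zeros kept: t / Mood |
|---|---|---|---|---|
| 20% v 10% | 8 v 8 | 1.6 v 0.8 | 4.7 / 6.0 | 33.2 / 47.0 |
| 30% v 15% | 8 v 8 | 2.4 v 1.2 | 4.7 / 4.8 | 49.2 / 68.2 |
| 40% v 20% | 8 v 8 | 3.2 v 1.6 | 5.0 / 5.4 | 62.4 / 83.8 |
| 60% v 30% | 8 v 8 | 4.8 v 2.4 | 5.0 / 4.9 | 84.6 / 98.4 |
| 20% v 10% | 8 v 10 | 1.6 v 1.0 | 13.3 / 9.6 | 19.3 / 45.8 |
| 30% v 15% | 8 v 10 | 2.4 v 1.5 | 16.8 / 10.2 | 27.5 / 68.9 |
| 40% v 20% | 8 v 10 | 3.2 v 2.0 | 20.2 / 12.5 | 35.5 / 85.2 |
| 60% v 30% | 8 v 10 | 4.8 v 3.0 | 27.8 / 16.7 | 53.9 / 98.4 |

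With equal stays, the admitted-only tests reject at about the nominal 5% although days per patient halve. With 8 v 10 they reject more often, but the mean difference points to longer stays on vaccine.

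**Step 3. A second set of assumptions.** Take 0.5 admissions per patient-year on placebo, half of 4 days and half of 12 (mean 8), and borrow the exacerbation ratio 0.4/0.7 = 0.571 for admissions.
- All types prevented equally: 0.5 × 8 = 4.0 v 0.286 × 8 = 2.29 days per patient; 8 v 8 per stay.
- Only short stays prevented: 0.036 × 4 + 0.25 × 12 = 3.14 days per patient against 4.0; 3.14/0.286 = 11.0 days per stay against 8.

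The second case is extreme: short admissions must fall from 0.25 to 0.036 per patient-year, a cut of 86%. It marks the direction of the distortion, not a likely size.

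**Step 4. Zeros kept.** If fewer than half of all patients are admitted, the pooled median is 0. With ties counted as not above the median, Mood's test then sorts patients into some days and no days, which is the share ever admitted. The table shows this: lengthening vaccine stays from 8 to 10 days leaves Mood's power almost unchanged (47.0 and 45.8; 68.2 and 68.9; 83.8 and 85.2), while the t test falls (33.2 to 19.3; 49.2 to 27.5; 62.4 to 35.5). When fewer than half of each arm are admitted, both medians are 0, so an absolute effect stated as a difference in medians is 0.

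**Step 5. Follow-up.** SAP 7.1.1 assumes 20-25% dropout: 0.20 × 90 = 18 to 0.25 × 90 = 22.5 patients per arm. Protocol 6.3.4 does not follow voluntary dropouts. A patient who leaves at month 6 with 5 days counts as 5, although the rate is 10 per patient-year. Neither planned test uses time observed. The exposure adjustment in SAP 7.4.1 is written for exacerbation counts only.

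**The case against.** A reader might infer that the SAP prescribes an analysis of admitted patients only. It does not. No unit and no exclusion are written. SAP 7.4 and 5.1.2 point to all randomised and dosed patients, and the visit schedule records a number of hospital days, which is naturally 0 for a patient not admitted. A known zero is not a missing value, so the no-imputation rule does not remove it. All of this stands: a per-patient total is a fair reading. But the analysis sets say who is eligible and do not supply a value, and the total-days reading has the faults in steps 4 and 5.

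A reader might also infer that prevented admissions would be lost from the trial. They would not. Number of admissions is tested in the same list, direct costs are there too, and the severity score in SAP 6.1.2 gives 3 or 4 points to hospitalisation. The difficulty lies in one variable, although days in hospital is an outcome in its own right and the count does not stand in for it.

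Nor is this a departure of the SAP from the protocol: protocol 10.1 has the same wording.

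Finally, the sizes are assumed throughout. That is correct, and they serve only to show direction and mechanism.

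**Conclusion.** The point holds as a gap in specification with a real consequence. Days in hospital for COPD exacerbations has no analysis under its own name, and the variable tested in its place is undefined in unit, zeros and cause. As length of stay, it would show nothing (rejection about 5-6% when days per patient halve) or longer stays on vaccine (8 v 10 while days per patient fall by 37.5%). As total days with zeros, Mood's test measures the share ever admitted when fewer than half are admitted, and neither test allows for unequal follow-up. These figures rest on assumed placebo admission shares of 20-60%, a halving by vaccine, and mean stays of 8 or 10 days. The documents do not support the stronger conclusion that an admitted-only comparison is planned or that the trial would miss an effect on admissions. This is a secondary outcome, and the correction is worth making before unblinding, so that the reading is not chosen with results in view.

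**What to change.** In SAP 7.4.2, replace the duration of admissions with: total hospital days caused by COPD exacerbations per randomised patient over the 12-month treatment period, zero if never admitted. Give the 18-month total as supportive. Make the same change in protocol 10.1 or record it as a deviation.

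Analyse it in the FAS by randomised arm with time observed as exposure, for example a count model with robust standard errors, or mean days per patient-year with a bootstrap interval. Report length of stay per admission and duration of episodes descriptively only, without a between-arm test.

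The cost is a few sentences. Table 1 in both documents already records hospital days at every visit to month 18. Protocol 8.2 names only visits 1-4 and should be aligned for the 18-month total. The downside is many zeros, so the interval will be wide.

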**All subjects will start treatment with Bactek vs. placebo in a stable clinical condition.**

- The subjects shall attend study visits every 3 months and whenever they develop symptoms of respiratory infection.
- They must strictly record the number of days of oral or systemic antibiotic treatment required until the remission of their ailment (COPD exacerbation).
- The number of days of hospitalization required due to the severity of the clinical condition (COPD exacerbation both during and after the immunization [6 months]) will be strictly recorded until the patient's clinical symptoms resolve and they are discharged home in a stable clinical condition.
- The pre- and post-immunization quality of life will be recorded using the specific CAT survey.
- Baseline Visit (prior to the start of the treatment)

The baseline visit can take place 1-4 weeks before the start of the treatment (visit 1), and the following tests will be performed that day (Table 1):

- Informed consent.

- Inclusion and exclusion criteria.
- Demographic data (including residence data).
- Vital signs (body temperature [BT] and HR).
- Tobacco consumption (no. of cigarettes/day x no. of years/20).
- Medical history/complete examination (description of the abnormality).
- Measured exhaled CO.
- Collection of blood samples to perform the following tests:
  - ~ Hematology
  - ~ Serum chemistry
  - ~ Viral serology testing
  - ~ Immunological assessment

A blood sample of each patient will be collected during the baseline visit for the following:

- Determination of serum levels of IgG, IgA, and IgM. In patients with IgG levels <500 mg/dl or IgA levels <6 mg/dl, a determination of the IgG subclasses will be performed (nephelometry, Beckmann Coulter, USA) to rule out an immunodeficiency.
- Serum concentration of the anti-pneumococcal and anti-tetanus toxoid antibodies. An *in vivo* response study will also be performed in patients with low levels of antibodies in order to rule out an immunodeficiency in antibody

production.

- Spirometry.
- Recording of concomitant medication.
- Pregnancy test (for women of childbearing age).
- Recording of the consumption of healthcare resources.
- Subject's visual analog scale score.
- Investigator's visual analog scale score.
- Quality-of-life questionnaire.
- Comments.
- CRF review.

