- The healthcare resources consumption will be recorded during all visits using the CRF.
- The number of days of antibiotic treatment required will be recorded during visits 1-4 using the CRF.
- A visual analog scale will be scored by the subjects during all visits and the result will be recorded in the CRF.
- A visual analog scale will be scored by the investigator during all visits and the result will be recorded in the CRF.
- The CAT Quality-of-Life Questionnaire will be completed during all visits.
- The Patient Diary will be provided during visits 1-4.
- The Patient Diary will be collected during visits 2-4.
- The sublingual vaccine will be dispensed during visits 1-3.
- The sublingual vaccine will be collected during visits 2-4.
- The number of days of hospitalization due to a COPD exacerbation will be recorded during visits 1-4.
- The CRF will be used for this purpose.
- The adverse events occurred during the trial will be recorded during visits 1-4. The CRF will be used for this purpose.

- Any unscheduled visit required due to COPD exacerbations will be recorded during visits 1-4.
- The CRF and CRF of unscheduled visits will be used for this purpose.
- The patients who dropped out from the trial during its course and the cause for the dropout will be recorded during visits 1-4. The CRF will be used for this purpose.
- Any observation deemed appropriate about any aspect of the trial will be recorded in the CRF during all visits.
- The trial monitor will review the CRF during all visits.

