7.1.7. Adjustments for Covariates

This study will use the draft guidance Adjusting for Covariates in Randomized Clinical Trials for Drugs and Biological Products - Guidance for Industry (CDER, May 2021, Revision 1). All baseline characteristics will be used to study exacerbations appearance in time using a Poisson regression or equivalent (see below).

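### The SAP tests CAT quality of life without naming a visit, saying whether a level or a change is compared, or using the pre-dose score, so precision already collected is lost.

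*SAP*

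**What the plan says.** The outcome is defined in SAP 6.1.2, and in near-identical words in Protocol 5.1, as "Health-related quality of life, as determined by an adapted version of the specific CAT test". Neither definition gives a time point, a change or a summary over visits.

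Protocol 8.2 states that "The CAT Quality-of-Life Questionnaire will be completed during all visits". Table 1 in both documents marks the questionnaire in all seven columns: the baseline visit and months 0, 3, 6, 12, 15 and 18. Protocol 5.2.1 gives the purpose: "The pre- and post-immunization quality of life will be recorded using the specific CAT survey".

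SAP 7.4.2 (and Protocol 10.1) names quality of life near the end of a list that also covers exacerbation counts and admissions: "immunological outcomes described in the trial design, quality of life, and direct costs". The rule for the whole list is "Differences between the means will be analyzed using Student's T test in the case of variables with a normal distribution". For anything judged non-normal, the plan switches to Mood's median test. A 95% CI for the absolute effect is required in all cases.

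Other adjusted analyses in the SAP have other targets. Section 7.1.7 says "All baseline characteristics will be used to study exacerbations appearance in time using a Poisson regression or equivalent", and 7.1.9 and 7.4.1 likewise attach covariates to the exacerbation model. The analysis of covariance in 7.4.2 is for the immunological variables. Protocol 10.1 allows adjustment of effects if confounding is detected; the SAP does not repeat this.

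**The concern.** The CAT is collected before and after immunisation, but no sentence says how the pre-dose score enters the analysis. A patient's later score usually tracks the earlier one to some degree. A comparison that ignores the earlier score leaves that stable between-patient variation in the error term and widens the confidence interval.

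The missing visit is a second gap. Of the five post-dose assessments, months 3, 6 and 12 fall on treatment and months 15 and 18 fall after it has stopped. With none designated, the visit to emphasise can be chosen after the results are seen. SAP 7.4.2 does list time points for exacerbations and for the immunological variables, so the omission for the CAT departs from the section's own practice.

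**Working it through.** **What the plan supplies.** It states no SD, correlation, power or detectable difference for the CAT, so there is no CAT figure to reproduce. The 90 per group in SAP 7.1.1 was set for exacerbations and serves here only to give the number evaluable: 90 × 0.75 = 67.5, taken as 67, and 90 × 0.80 = 72 per arm at the stated 25% and 20% dropout.

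**Assumptions.** r is the correlation between a pre-dose and a later CAT score. It is not in the documents, so a range of 0.3 to 0.7 is shown. For the average of two pre-dose scores, the same r is assumed between all CAT occasions. Tests are two-sided at 0.05. Effects are in units of the between-patient SD.

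**Variance of the treatment difference, relative to an unadjusted comparison of post-dose levels**

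- One pre-dose score as covariate: 1 − r²
- Mean of two pre-dose scores as covariate: 1 − 2r²/(1 + r)

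For example, at r = 0.5: 1 − 0.25 = 0.75, and 1 − 0.50/1.5 = 0.667. The CI width ratio is the square root.

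| Assumed r | Variance cut, one score | CI narrower by | Variance cut, mean of two | CI narrower by |
|---|---|---|---|---|
| 0.3 | 9% | 5% | 14% | 7% |
| 0.4 | 16% | 8% | 23% | 12% |
| 0.5 | 25% | 13% | 33% | 18% |
| 0.6 | 36% | 20% | 45% | 26% |
| 0.7 | 49% | 29% | 58% | 35% |

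**Difference detectable with 80% power.** This is (1.96 + 0.84) × √(2/n) × residual SD.

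- Unadjusted: 2.80 × √(2/67) = 0.48 SD, or 2.80 × √(2/72) = 0.47 SD.
- One pre-dose score, 67 and 72 per arm: 0.46 and 0.45 SD at r = 0.3; 0.42 and 0.40 at r = 0.5; 0.35 and 0.33 at r = 0.7.

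**Power for an illustrative true effect of 0.4 SD (67 to 72 per arm)**

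- t test on post-dose levels: 64% to 67%.
- Analysis of covariance, one pre-dose score: 68% to 71% at r = 0.3, 76% to 79% at r = 0.5, 90% to 92% at r = 0.7.
- Mood's median test on roughly normal data (asymptotic efficiency 2/π = 0.64): about 46% to 48%.

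**A simple change score.** Its variance relative to the unadjusted level comparison is 2(1 − r): 1.40 at r = 0.3, 1.00 at r = 0.5 and 0.60 at r = 0.7. It is therefore less precise than ignoring baseline when r is below 0.5. Analysis of covariance has no such region in large samples.

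**Room for selection across visits.** Simulating five equally correlated null comparisons, each tested at 0.05, gives a chance of at least one nominally significant result of 21%, 18%, 15% and 13% when the correlation between visits is assumed to be 0.3, 0.5, 0.7 and 0.8. This is what could happen if the visit were picked after the fact. Nothing in the documents says that it will be.

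**The case against.** The strongest reply is that nothing here is biased. Allocation is 1:1 and randomised, so a post-dose comparison without baseline is valid, and its 95% CI already reflects chance imbalance. That stands. A reader might infer that between-patient differences will hide a real effect or distort the estimate; the documents support only a loss of precision.

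A reader might also infer that the SAP prescribes a comparison of raw levels. It does not say so. A test of mean change would also fit the wording, given the stated pre- and post-immunisation purpose. The defect is that the choice is left open.

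Three provisions bear on the point, and none closes it:

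- Protocol 10.1 adjusts if confounding is detected. That depends on the data, does not name the CAT, and is absent from the SAP.
- SAP 7.1.7 opens by adopting general guidance on covariate adjustment, but its specific instruction covers exacerbations only.
- SAP 7.1.5 offers Holm adjustment if multiple comparisons are needed, which does not fix the visit.

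An adjusted CAT analysis is not excluded either: the immunological outcomes appear both in the t-test list and under analysis of covariance. Still, none is specified for quality of life.

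Finally, it is tempting to say that two CAT scores precede the first dose. Only the baseline-visit score, taken 1 to 4 weeks before treatment, is clearly pre-dose. The first dose is given at visit 1. Protocol 5.2.1 lists the questionnaire before vaccine delivery at that visit, but no text states that order of events.

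**Conclusion.** The point holds as underspecification with a cost in precision. The SAP names neither the CAT visit nor the quantity compared, and it makes no use of the pre-dose score; no other section supplies these.

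The size depends on a correlation that the documents do not give. It is small at r = 0.3 and substantial at r = 0.7, and the two-score figures also assume equal correlations between occasions. The gains are measured against an unadjusted comparison of levels, which is one reading of the SAP. The gap over the visit does not depend on r.

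This is a free improvement of low priority: it concerns one secondary outcome, and the trial is not powered on the CAT.

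**What to change.** In SAP 6.1.2, define the quality-of-life outcome as the CAT score at month 12, the end of treatment.

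In SAP 7.4.2, take quality of life out of the generic t-test or median-test rule. Compare the arms by analysis of covariance with the baseline-visit CAT as covariate, and report the adjusted mean difference with its 95% CI. If site procedures confirm that the visit-1 CAT is completed before the first dose, use the mean of the two scores as covariate. Label months 3, 6, 15 and 18 as supportive, under the same model. A repeated-measures model over months 3 to 12 with the same covariate would also serve, provided that month 12 is named as the contrast of interest.

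The same paragraph should say how a missing month-12 CAT is handled, because Protocol 10.5 carries the last observation forward while SAP 7.1.2 imputes nothing.

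The cost is SAP wording only. The scores are already scheduled, and the SAP already uses analysis of covariance for other variables.

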5.2. Inclusion–Exclusion Criteria and General Study Population

A total of 198 subjects will be screened from the Respiratory Departments of participating centers.

These screened subjects will have been diagnosed with moderate or severe COPD.

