7.1.1. Sample Size and Power

The calculation of the sample size is based on the efficacy measured based on the decrease in the number of episodes of COPD exacerbations during the 12-month treatment period of the trial per subject.

The ratio of subjects to be distributed among the active treatment and placebo groups will be 1:1.

We estimate that subjects from group I (active treatment with the bacterial vaccine) will achieve a 60% decrease in their number of COPD exacerbations compared with a 30% decrease among those of group II (placebo). With an alpha error of 0.05 and a beta error of 0.2, and assuming a dropout rate of 20-25%, the number of subjects to be recruited would be 90 per study group, with an overall total of 180 trial subjects.

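### SAP 7.4.2 studies exacerbations by COPD severity group but plans no comparison of the treatment effect between the groups

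*SAP*

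**What the plan says.** SAP 7.4.2 (Secondary Efficacy Analysis) contains two severity-group analyses. For the count: "Number of exacerbations will be studied in the mild, moderate and severe COPD populations at 3, 6, 12 months and whole study". For first exacerbation, after listing the same four limits for the ITT and PP sets: "these same limits will be studied in the moderate and severe COPD populations". That makes 3 × 4 = 12 plus 2 × 4 = 8, so 20 group-by-time results, before SAP 7.4 applies the efficacy analyses to all analysis sets.

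The same section lists number of exacerbations among the variables to be compared between arms by Student's t or Mood's median test, with a 95% CI for the absolute effect.

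The count model in SAP 7.1.7, 7.1.9 and 7.4.1 is a Poisson regression with baseline characteristics as covariates. No product of treatment and severity is mentioned. Protocol 10.1 plans no severity groups, so the SAP adds them. Randomization (Protocol 5.3.1, SAP 7.1.4) is in blocks of 6, with no mention of stratification by severity.

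On who is eligible, SAP 5.2 says: "These screened subjects will have been diagnosed with moderate or severe COPD". A mild population therefore appears in the analysis but not in the entry criteria.

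**The concern.** A significant result in one severity group and a non-significant one in another is not evidence that the effect differs. Each group holds only part of the sample, so each has less power than the whole trial, and discordant p-values are common even when the effect is identical. As written, the plan gives a reader nothing else by which to judge whether severity modifies the effect. A covariate main effect does not answer that question.

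At stake is a sentence in the report saying that the vaccine works in one severity class and not in the other, when the data do not distinguish the two.

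**Working it through.** **Inputs from the documents.** SAP 7.1.1 gives "With an alpha error of 0.05 and a beta error of 0.2", a 60% vs 30% decrease, 20-25% dropout, 1:1 allocation, and "the number of subjects to be recruited would be 90 per study group, with an overall total of 180 trial subjects". Evaluable per arm: 90 × 0.75 = 67.5 to 90 × 0.80 = 72.

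**Assumptions.** The severity split, the baseline rate and the dispersion are not given. The tests are taken as two-sided. The split is varied from 50/50 to 90/10.

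**The plan's own sample size.** Treating 30% vs 60% as proportions (two-sided 0.05, 80% power) gives 42 per arm, or 53-56 after dropout. With continuity correction it is 49 (62-66); one-sided, 33 (42-44). None gives 90. With 67-72 evaluable per arm, power for 30% vs 60% is 94.6-95.9%. A calculation on counts cannot be checked without a rate and a dispersion. Overall power is therefore carried as a range, 80% (as stated) to about 95%.

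**Chance that exactly one of two groups is significant under an identical effect.** The whole-trial noncentrality is z(0.975) + z(power). A group with share f has this multiplied by √f. With group powers p1 and p2, the chance is p1(1 − p2) + p2(1 − p1).

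- 80% power, equal halves: (1.960 + 0.842) × √0.5 = 1.981. Power per group is Φ(1.981 − 1.960) = 0.508, and 2 × 0.508 × 0.492 = 50.0%.
- 95% power, equal halves: (1.960 + 1.645) × √0.5 = 2.549. Power per group is Φ(0.589) = 0.722, and 2 × 0.722 × 0.278 = 40%.

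| Split | 80% overall power | 30% vs 60% as proportions, 67-72 per arm |
|---|---|---|
| 50/50 | 50.0% | 39-42% |
| 60/40 | 51.2% | 42-44% |
| 70/30 | 54.9% | 49-51% |
| 80/20 | 60.8% | 62-63% |
| 90/10 | 68.3% | 77% |

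With 90 per arm and no dropout, the proportions calculation gives 28.5% at 50/50.

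**Check by simulated counts.** Take three prior-year exacerbations (one of the two entry routes) as an assumed baseline. The means are then 3 × 0.70 = 2.1 (placebo) and 3 × 0.40 = 1.2 (active), a rate ratio of 0.57.

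- Robust Poisson with log follow-up time, 45 per arm in each of two groups, 22.5% dropout, dispersion from 0.4 to 1.0, 4,000 trials per setting: exactly one group significant in 39.8%, 48.7% and 50.2%. The interaction test was wrongly significant in 5.4%, 5.6% and 5.8%.
- Same set-up with Mood's median test: 48%, 43% and 39%. The size is similar, but the trend with dispersion reverses.
- Same rates, robust Poisson, 90/10 split: 64-69%. The interaction test rejects in about 8-9%, since the small group then has only 9 per arm before dropout.
- Mann-Whitney, 68-72 per arm, equal halves: 50-53% at dispersion 0.5, 45-47% at 1.0, and 30-32% with no over-dispersion. With no over-dispersion and no dropout (90 per arm) it falls to 18%.

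**Power of the interaction test.** If the overall estimate has standard error s, each half has s√2 and their difference has 2s. For a between-group difference equal to the overall effect at 80% overall power, the noncentrality is 2.802 / 2 = 1.401, and power is about Φ(1.401 − 1.960) = 29%.

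**The case against.** The SAP says the groups will be studied. It does not say that arms will be tested within each group, and it nowhere tells the reader to compare p-values across groups. SAP 7.1 states that the analysis uses no significance levels, SAP 7.1.5 confines multiple comparisons largely to exploratory use, and SAP 7.4.2 already promises confidence intervals.

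Part of this stands. Testing within groups is an inference from the section in which the sentence sits, not an explicit instruction. But that section names between-arm tests for this very variable, and Protocol 10.3 sets alpha at 0.05. The disclaimer in SAP 7.1 is followed directly by a sentence about a histamine concentration, which is not an endpoint of this trial. Holm adjustment, even if applied, would not compare the groups.

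Three stronger readings are not supported:

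- A reader might infer that an identical effect will look different in 40-50% of trials without conditions. The figure needs an equal split that the documents do not give. It also means only significant in one group and not in the other. Estimates in opposite directions are rare: about 5% at 80% power with equal halves.
- A reader might infer that four time limits make the figure worse. The windows overlap and are correlated, and no figure for them jointly was calculated.
- A reader might infer that the sponsor intends a severity-specific claim, or that mild patients were enrolled. Neither document says so.

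**Conclusion.** The point holds as a gap in a secondary analysis. Severity-group results are planned at four limits, and the effect is never compared between groups. If the results are read by significance, two about equal groups would disagree in about 40-50% of trials under an identical effect, at overall power of about 80-95%. Across splits and dropout, the proportions calculation runs from about 28% to 77%; only counts without over-dispersion and without dropout fell clearly lower. An interaction test errs in about 5-6% with equal groups, and about 8-9% for robust Poisson at 90/10. The primary analysis is not affected.

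**What to change.** In SAP 7.4.2:

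1. Add a treatment-by-baseline-severity term to the count model already planned in SAP 7.4.1, in the FAS, at month 12.
2. Report the rate ratio with 95% CI in each severity group as descriptive only, and make no group-specific claim without the interaction result.
3. Reconcile the mild population with the moderate-or-severe eligibility in SAP 5.2 and 5.2.1, and define the groups from baseline data. Using FEV1 % predicted as a continuous modifier is possible, but the stated 30-50% entry range leaves it little leverage.

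The cost is SAP wording and one model term. The downside is low power: about 29% for a between-group difference as large as the overall effect, with equal halves. A non-significant interaction would therefore not show that the effect is the same in both groups; the width of the confidence intervals will make this visible.
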